## **Brief Study Synopsis**

**Study Phase:** Pilot

**Primary hypothesis:** Pentoxyfylline (PTX) therapy at 1200 mg per day or the renally dose equivalent in addition to standard of care is superior to placebo in the treatment of acute renal failure (ARF) not responsive to volume resuscitation in hospitalized patients with cirrhosis.

**Study design:** Prospective, placebo-controlled, randomized pilot trial.

Each hospitalized subject will undergo pre-dosing screening with review of his or her history and physical exam from the day of enrollment and safety assessment to ensure no contraindication to use of PTX.

ARF will be defined according to the definition put forth by and validated prospectively by collaboration between the International Ascites Club (IAC) and the Acute Dialysis Quality Initiative as a rise in creatinine of 0.3 mg/dl or 50% from baseline creatinine, which will be defined as the most recent stable measurement before admission.[1]

Baseline testing will be obtained from hospitalization records, including but not limited to chemistry panel, liver function testing, urinalysis, urine electrolytes, coagulation studies, blood cultures, chest x-ray, diagnostic paracentesis, abdominal ultrasound with Doppler.

Subjects will take either placebo three times a day or PTX 400mg three times a day or 400mg twice a day for eGFR 10-50 and 400mg once a day for eGFR <10 for 14 days in addition to standard inpatient care. Treatment will be continued for 14 days unless a study endpoint has been reached at which time either PTX or placebo will be stopped.

**Total study subjects expected:** 30 patients with cirrhosis hospitalized ARF

**Duration of study:** 180 days

**Study Drugs:** PTX 400 mg tablets and placebo. The study team will not be pursuing a change in labeling or an FDA approved indication for this drug as a part of this proposal. Standard placebo provided in similar tablet forms. All investigational drugs will be prepared by the Investigational Pharmacy by inserting the active drug/placebo into larger cloaking capsules. Standard corn starch will be used inside the placebo capsule.

Randomization will be 1:1. The Investigational Pharmacy will be performing randomization and will generate the block randomization scheme.

**Endpoints:** The primary endpoint is resolution of ARF, defined as a return to baseline creatinine for 24 hours.

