The secondary endpoints of progression of ARF to a different stage as defined by AKIN criteria will be assessed.[3] If a patient is enrolled at stage III ARF, they will be considered to have progressed should they be started on renal replacement therapy (RRT). Other secondary endpoints that will be assessed include change in serum creatinine from baseline to day 14, combined increase of treatment success and “partial response” which we define as serum creatinine level decreased by >50% from baseline but not to baseline without dialysis or HRS recurrence, transplant free survival at day 30 and 180, overall survival at day 30 and 180, composite survival index at day 30 and 180.

**Statistical Methods:** All analyses will be conducted based on the intention to treat population. Results will be expressed as means with standard deviations. Chi-squared and Fisher’s exact test will be used to analyze our categorical endpoints. Student’s t test and Mann-Whitney Rank Sum test will be used for secondary analysis of differences in numerical lab data. Kaplan-Meier curves will be constructed and compared by a log-rank test to assess our secondary endpoints of survival. A p value of <0.05 will be significant. Subgroup analysis will be performed by stratifying on initial AKIN stage.

**Future Study:** If there is a treatment benefit with using PTX for treatment of ARF in patients with cirrhosis, we would apply for an orphan grant from the NIH or foundation awards from the American Association for the Study of Liver Diseases for a multi or single center, randomized, double blinded placebo controlled trial. Ideally we could combine this with translational research to help better determine a mechanism of action.

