## 8. Study Assessments

### 8.1. Schedule of Visits

The schedule of study assessments and visits is shown in Table 2.

Table 2: Schedule of visits and study protocol assessments

Visit	Screening initial assessment	Follow up assessment	"Partial response" assessment	Phone Call
Day	0	Day 3,7,10,14	Day 14, 28	Day 30,180
Initial history and physical exam	X			
ARF response assessment		X	X	X
Symptom triggered physical exam		X	X	
Interim safety assessment and pill count		X	X	
Labs and imaging	X	X	X	

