## 9. Statistical Procedures and Methods

As this is a pilot study and the benefit of PTX in the treatment of ARF has not been studied, we estimate a sample size of 30, 15 in each treatment arm, is sufficient to meet our primary and secondary endpoints. Results will be expressed as means with standard deviations. Chi-squared and Fisher's exact test will be used to analyze our categorical endpoints. Student's t test and Mann-Whitney Rank Sum test will be used for secondary analysis of differences in numerical lab data. Kaplan-Meier curves will be constructed and compared by a log-rank test to assess our secondary endpoint of all-cause mortality. A p value of  $<0.05$  will be significant. Intention to treat analysis will be performed. Subgroup analysis will be performed by stratifying on initial AKIN stage.

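### With baseline creatinine defined only as the pre-admission value, partial response as written is empty or not sensible, and the day-14 creatinine change has two possible values

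*Combined protocol and SAP*

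**What the plan says.** The Brief Study Synopsis and Section 3 define ARF as a rise of 0.3 mg/dl or 50% from "baseline creatinine, which will be defined as the most recent stable measurement before admission". No other definition of baseline creatinine appears. The primary endpoint uses that term: "The primary endpoint is resolution of ARF, defined as a return to baseline creatinine for 24 hours".

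Two secondary endpoints, worded identically in the synopsis and Section 5.2, use the word without qualification:

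- Partial response, which is combined with treatment success: "serum creatinine level decreased by >50% from baseline but not to baseline without dialysis or HRS recurrence". Treatment success is not defined.
- The numerical creatinine endpoint: "change in serum creatinine from baseline to day 14".

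The synopsis also uses the word in a second sense, for in-hospital tests: "Baseline testing will be obtained from hospitalization records, including but not limited to chemistry panel". Table 2 (Section 8.1) lists "Labs and imaging" at day 0 and schedules a partial-response assessment at days 14 and 28. Neither Table 2 nor Section 9 says which creatinine is the reference. For numerical laboratory data, Section 9 plans Student's t test, and "Mann-Whitney Rank Sum test will be used for secondary analysis of differences in numerical lab data".

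**The concern.** In the partial-response rule the same word is both the value from which creatinine must fall and the value it must not reach. Only one baseline creatinine is defined, and it is the target of recovery. Using it as the starting point as well makes the rule fail. Table 2 shows that partial responders are nevertheless expected.

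The day-14 change has no such contradiction to force a reading. Measured from the pre-admission value it is residual elevation; measured from enrolment it is improvement since entry. Both can be computed and they answer different questions. If the reference is not fixed beforehand, it can be chosen after results are known, and the reported difference and p value depend on that choice.

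**Working it through.** Let b be pre-admission, e enrolment and c follow-up creatinine, in mg/dl. The plan gives no figure of its own to reproduce here.

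**1. Partial response with the defined baseline in both places**

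- A fall of more than 50% from b means c < 0.5b.
- If *not to baseline* means that creatinine stays above b, then c > b. No b > 0 satisfies both. A grid in 0.1 steps (b 0.4 to 3.5, e up to 4.0, c 0.1 to 6.0, keeping pairs that meet the entry rule) has 593 (b, e) pairs and 593 × 60 = 35,580 cases; 0 qualify. Table 1 prints the 4.0 limit in g/dL; mg/dl is assumed.
- If it means only that the 24-hour primary endpoint was not met, a subject qualifies by falling below 0.5b for under 24 hours. With b = 1.0, that is a brief dip below 0.5.

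**2. Partial response with the fall measured from enrolment**

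The conditions become c < 0.5e and c > b.

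- b 1.0, e 3.0, c 1.4: (3.0 − 1.4)/3.0 = 53%, and 1.4 > 1.0, so this is a partial response.
- If e ≤ 2b, then c < 0.5e ≤ b, so a fall of more than 50% always takes creatinine below b. Partial response while still above b needs e > 2b, which holds with a qualifying c in 240 of the 593 grid pairs. That is a count of grid points, not a forecast of patients.

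**3. Brief return to baseline, fall measured from enrolment**

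- b 1.0, e 1.9, c 0.9 for under 24 hours: (1.9 − 0.9)/1.9 = 53%. This is not resolution; it is a partial response or not depending on what *not to baseline* means.
- b 1.0, e 1.9, c 1.0 for under 24 hours: (1.9 − 1.0)/1.9 = 47%. This is neither resolution nor partial response on either meaning, although 1.0/3.0/1.4, still 40% above baseline, is a partial response.

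**4. Day-14 change**

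- The readings are c − b and c − e. They differ by (c − b) − (c − e) = e − b.
- For anyone still meeting the ARF definition at enrolment, e − b ≥ min(0.3, 0.5b), which is 0.3 when b ≥ 0.6.

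| Subject | b | e | day 14 | from b | from e |
|---|---|---|---|---|---|
| A | 1.0 | 3.0 | 1.4 | +0.4 | −1.6 |
| B | 1.5 | 1.8 | 1.5 | 0.0 | −0.3 |

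B does better on the first reading, A on the second.

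**5. Between arms (illustrative)**

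The two treatment estimates differ by the arm difference in mean e − b. Under randomisation its expectation is 0. With 15 per arm its SE is SD × √(2/15) = 0.365 × SD. The documents give no SD, so a range is assumed:

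- SD 0.5: SE 0.183; 1.96 × SE = 0.36 mg/dl.
- SD 1.0: SE 0.365; 1.96 × SE = 0.72 mg/dl.

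This takes all 30 subjects to have a day-14 value.

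**The case against.** The best defence is that the intent is plain. In-hospital tests are called baseline testing, Table 2 has day-0 laboratory work, and an interval running to day 14 suggests a start at enrolment. An analyst would probably use the enrolment value for partial response, since the alternative fails. That stands as a statement of likely intent. It does not settle the matter, because it departs from the only definition given and nothing compels the same departure for the day-14 change.

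A reader might infer that nobody could ever be a partial responder. The documents support that only if *not to baseline* refers to the creatinine level. On the 24-hour meaning the category is not strictly empty, though those in it are not sensible partial responders.

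A reader might also infer that the treatment comparison is biased, or that the 0.36 and 0.72 mg/dl figures are properties of this trial. Neither is supported. Both creatinine values precede treatment, so the discrepancy averages zero over randomisation. The SDs are assumed, and day-14 values may be incomplete: Section 2 leaves repeat blood work to the treating physicians, withdraws subjects discharged without an endpoint, and has no in-person follow-up after discharge.

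Finally, a reader might infer that naming the enrolment value makes the endpoint coherent at every enrolment level. It does not, as steps 2 and 3 show.

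**Conclusion.** The point holds and should be fixed. As written, partial response either has no members (0 of 30) or admits only subjects who dip briefly below half of their pre-admission value. On the first meaning, with treatment success taken as resolution, the combined endpoint is identical to the primary endpoint. The day-14 change has two values, at least 0.3 mg/dl apart in each subject still meeting the ARF definition at enrolment with a pre-admission value of 0.6 or more, and the choice can reverse the order of subjects.

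Two secondary endpoints of a pilot are affected. The primary endpoint's reference value is defined and is not in question. The algebra needs no assumption beyond the documents' own definitions; only the between-arm figures do, and they are illustrations.

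**What to change.** Before unblinding, amend the synopsis and Section 5.2, and carry the terms into Section 9:

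1. Define an enrolment creatinine separately from the pre-admission baseline, for example the last in-hospital value before the first dose. A rule for picking the value is needed: the synopsis takes these tests from hospitalization records, so a pre-dose measurement on day 0 is not guaranteed.
2. State that the fall of more than 50% and the day-14 change are measured from enrolment, and that the level not to be reached is the pre-admission value.
3. State that treatment success is the primary endpoint, and say how a return to baseline held for under 24 hours is classified.
4. Acknowledge that with a fall of more than 50% from enrolment, a subject whose enrolment creatinine is at most twice the pre-admission value cannot be a partial responder while still above baseline, and state whether that is intended.

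The cost is wording only. The pre-admission value is already needed for eligibility, and the enrolment value would be taken from the hospital record.

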## 1. Introduction and Study Rationale

Chronic liver disease (CLD) is the 12th leading cause of death in the U.S.[8] and is a significant cause of morbidity and hospitalizations across the world. It has been estimated that chronic liver disease represents yearly economic costs in upwards of \$2 billion.[9, 10] Acute renal failure (ARF) is one of the most common complications in patients with cirrhosis and leads to poorer outcomes.[11] The onset of ARF is typically in association with other manifestations of hepatic decompensation including gastroesophageal variceal bleeding, spontaneous bacteria peritonitis (SBP), hyponatremia and issues with volume status and can occur in up to 19% of patients hospitalized with cirrhosis.[12] ARF in patients with cirrhosis can be further subtyped into pre-renal azotemia (PRA), acute tubular necrosis (ATN) or Type I or II hepatorenal syndrome (HRS).[13]

HRS is a feared complication of CLD and cirrhosis and presents a unique challenge to physicians and their management. The incidence of HRS in patients with cirrhosis and ascites is 18 and 39 percent at one and five years, respectively.[14] HRS occurs in the absence of underlying kidney disease and leads to renal failure secondary to compensatory renal vasoconstriction due to an ineffective interarteriolar blood volume resultant from splanchnic arterial vasodilation.[15, 16] The prognosis of type 1 HRS is so poor with life expectancy less than 2 weeks.[7] Patients often decompensate and die prior to liver transplant (LT)

The standard of care to treat type I HRS is the combination of albumin, octreotide and midodrine.[17] Terlipressin in combination with albumin is also effective, however, this is not FDA approved or available currently in the U.S.[18] Noradrenalin and albumin may also be used however this requires ICU level care and is not applicable for all patients or all hospitals. [19] Patients who develop HRS and survive are more likely to develop HRS recurrence. After the withdrawal of treatment for type 1 HRS, recurrence can occur in up to 20% of cases.[17] Treatment for PRA or ATN is largely supportive with careful attention to volume status and avoidance of nephrotoxins.

Pentoxifylline (PTX) is a phosphodiesterase inhibitor with anti-inflammatory capabilities that lowers blood viscosity and improves erythrocyte flexibility. Proinflammatory cytokines, including TNF-a and interleukin-6 are elevated in patients with chronic liver disease and cirrhosis in response to circulating endotoxemia.[20, 21] These cytokines lead to a proinflammatory, hyperdynamic state in cirrhosis.

PTX has been shown to decrease levels of TNF-a[22] and has also been shown to increase systemic vascular resistance to oppose the splanchnic vasodilation seen in cirrhosis, but has not had a documented effect on portal pressures.[23]

PTX has is effective in preventing HRS in acute alcoholic hepatitis.[24] In their study of 101 patients, Akriviadis et al demonstrated that compared to placebo, patients randomized to 400mg PTX orally three times a day not only had improved survival

(24.5% versus 46.1% mortality,  $p = 0.037$ ; RR 0.59, 95% CI 0.35-0.97) but a decreased risk of developing HRS as a cause of death (50% versus 91.7% respectively,  $p = 0.009$ ; RR 0.29; 95% CI 0.13-0.65). Interestingly, the authors noted that increasing TNF- $\alpha$  levels during the hospital course were associated with an increase in mortality rate.

PTX has been used to treat renal failure from idiopathic membranous glomerular nephropathy[25] and to prevent GFR decline in high-risk chronic kidney disease patients when compared to placebo and thus may have a role in intrinsic kidney disease as well.[26]

Two studies have examined using PTX for HRS prevention in all cirrhotics. In their randomized controlled trial of 335 patients with advanced cirrhosis (Child-Pugh class C), Lebrec et al[27] demonstrated that the proportions of patients without a composite of complications, including HRS, were higher in the PTX group than the placebo group at two (78.6% vs. 63.4%,  $p = .006$ ) and six months (66.8% vs. 49.7%,  $p = .002$ ) respectively. Furthermore, the probability of being free of renal failure was statistically significant at 6 months in the PTX group (90.9%, 95% CI 86.1-95.6) versus the placebo group (79.4%, 95% CI 72.6-86.1%),  $p = 0.02$ . However, there was no appreciable survival difference at 2 and 6 months between these two groups.

In their landmark study, Tyagi et al[28] demonstrated that PTX is effective in preventing HRS in cirrhotic patients with ascites. In their randomized placebo controlled trial of 70 patients, 35 were given PTX with improvements in serum sodium, mean arterial pressure and preservation of creatinine. Of the 12 patients who developed HRS, two patients were in the PTX arm (type-1 HRS,  $n = 2$ ) ( $P = 0.01$ ). The authors noted that patients with HRS had higher baseline TNF- $\alpha$  ( $15.3 \pm 5.8$  vs.  $10.9 \pm 4.8$  pg/ml,  $P = 0.01$ ), lower MAP ( $68.0 \pm 3.8$  vs.  $77.8 \pm 6.5$  mmHg,  $P = 0.01$ ), and sodium level ( $131.2 \pm 3.0$  vs.  $135.6 \pm 4.7$  mmol/l,  $P = 0.003$ ) than those who did not develop HRS.

To our knowledge, no study to date has investigated adding PTX to the treatment algorithm for the treatment of ARF in patients with cirrhosis despite the previously demonstrated benefit of PTX as primary prophylaxis to prevent HRS, a subtype of ARF.[27]

For all of these reasons, we propose a double blind, randomized, placebo controlled pilot trial with PTX to investigate the efficacy of PTX in treating ARF in patients with cirrhosis.

## 2. Study Design

[figure not shown]
The proposed study is a blinded prospective, placebo controlled, randomized pilot study. Figure 1 shows the study design schematic. Subjects will be identified during their hospitalization with ARF. Each subject will undergo screening and a pre-dosing history and physical exam, and safety assessment, which will include reviewing basic blood work results and imaging from their hospitalization (CBC, CMP, INR, Blood cultures, UA and urine culture, Urine lytes, Chest x-ray, Abdominal ultrasound with dopplers, diagnostic paracentesis if ascites is present) and performing urine pregnancy testing in women of child bearing potential. Subjects will be randomized 1:1 by the Investigational Pharmacy.

Subjects will then take a 14-day course of PTX 400 mg three times a day. On day 3 there will be an in-person assessment and review of side effect profile. If there have been no serious adverse events, PTX will be continued. Additional safety assessments will be completed at day 7,10,14.

Patients will also be seen in the hospital to assess for treatment response at day 3,7,10,14. At these visits, they will have repeat blood work at the discretion of the treating physicians (e.g. CBC, CMP, INR, UA with reflex urine culture, Urine lytes,). During each assessment, primary and secondary endpoints will be measured. If an endpoint is obtained, the patient will be instructed to stop therapy.

Survival will be assessed at 30 and 180 days by telephone interviews. If subjects are discharged prior to completing 14 days of therapy, they most likely has met an endpoint (resolution, death, transplant, etc). If in the unlikely event the patient is to be discharged and they have not met an endpoint, they will be withdrawn from the study. Once the patient is discharged there will be no in person follow up evaluations.

Figure 1: Study protocol

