## 7. Study Treatments

### 7.1. Investigational Drug

PTX is a vasoactive xanthine derivative and phosphodiesterase inhibitor that improves peripheral blood flow and enhances peripheral tissue oxygenation. PTX relaxes smooth muscle in peripheral vessels leading to vasodilation. PTX improves red blood cell flexibility, which allows for improved blood flow ability. Importantly, PTX promotes platelet deaggregation and decreases blood viscosity. The summative effects are a decrease in inflammatory mediators. The investigational pharmacy will be used for drug acquisition, storage, and accountability. Subjects will start the protocol with 400mg PTX three times a day for 14 days or the renally dosed equivalent (400mg BID for eGFR 10-50 and 400mg daily for eGFR <10). The investigators will not seek FDA labeling or approved indications for PTX as part of this study; therefore, no IND will be sought for the study drug use in this protocol. There are no restrictions on concurrent drugs other than those listed in the exclusion criteria in Table 1. The study drug cannot be crushed or administered through a nasogastric tube. If a patient is NPO but can swallow safely, they may receive the drug. If they are NPO and have a nasogastric tube in place they will miss the dose.

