### 7.2. Study Drug Discontinuation

Study drug or placebo will be discontinued if a grade 3 adverse event (based on the NCI Common Terminology Criteria for Adverse Events, CTCAE, version 4.0) related to the study drug at the judgment of the PI and medical monitor. The PI will notify the medical monitor of a grade 3 adverse event over the phone and the medical monitor will conduct an independent review with access to the medical record. The medical monitor may interview the patient at the bedside should they deem this necessary. Meetings between the medical monitor and the PI will take place on an as needed basis. One scheduled meeting will take place after 50% enrollment has been completed to review all the reported adverse events.

Study drug or placebo will be discontinued if a grade 4 adverse event or pregnancy occurs during the study protocol or at the request of the subject. If the subject misses a dose and is less than 4 hours late, the subject will be advised to make up the dose. Otherwise, the dose can be omitted and per protocol dosing can resume with the next scheduled administration.

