### 8.2. Primary Endpoints

ARF treatment response will be assessed according to Table 2. The PI or sub-investigators will perform all assessments and will assess for the presence of side effects or toxicities of the study drug by performing a brief history at each visit and by performing a targeted physical exam. A phone call to assess 30 and 180-day survival will be completed.

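### The synopsis reduces PTX frequency by eGFR but gives placebo only as three times a day, so at eGFR 50 or below capsule frequency can reveal the arm

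*Combined protocol and SAP*

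**What the plan says.** Three places describe the regimen.

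- **Brief Study Synopsis:** "Subjects will take either placebo three times a day or PTX 400mg three times a day or 400mg twice a day for eGFR 10-50". The sentence goes on to once a day for eGFR below 10, all for 14 days. The placebo frequency carries no eGFR tier. The primary hypothesis in the same section also allows for a renally adjusted dose.
- **Section 7.1 (Investigational Drug):** PTX three times a day or a renal equivalent, "400mg BID for eGFR 10-50 and 400mg daily for eGFR <10". Placebo frequency is not mentioned.
- **Section 2 (Study Design):** "Subjects will then take a 14-day course of PTX 400 mg three times a day". There is no renal tier and no mention of placebo.

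On masking, section 1 says "we propose a double blind, randomized, placebo controlled pilot trial with PTX", and section 2 also calls the study blinded. The one masking measure described is "inserting the active drug/placebo into larger cloaking capsules", with corn starch in the placebo capsule.

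On who sees the dosing, Table 2 in section 8.1 lists "Interim safety assessment and pill count" at the in-person follow-up assessments (days 3, 7, 10 and 14). Section 8.2 states: "The PI or sub-investigators will perform all assessments".

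**The concern.** Over-encapsulation makes one capsule look like another. It does nothing about the number of capsules a day. If PTX is reduced at low eGFR and placebo is not, the schedule itself differs between arms in that group.

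Every subject has acute renal failure, so reduced eGFR will not be a rare exception. The investigators who assess subjects also meet the capsule counts, and eGFR follows from the creatinine they are already following.

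The primary endpoint is a laboratory creatinine, which leaves little room for biased assessment. Other steps leave more room:

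- starting renal replacement therapy, which counts as progression for a subject enrolled at stage III;
- concurrent drugs, which section 7.1 leaves unrestricted apart from the exclusions in Table 1;
- whether a grade 3 event is "related to the study drug at the judgment of the PI and medical monitor", which decides whether study drug stops.

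**Working it through.** **Inputs.** 400 mg per dose, 14 days and the PTX frequencies by eGFR (synopsis and section 7.1); placebo three times a day (synopsis); 30 subjects (section 9). I take one 400 mg tablet per cloaking capsule. The plan gives no figure of its own on this point to reproduce.

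**Step 1: scheduled capsules by arm under the synopsis.** Capsules = doses per day × 14.

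| eGFR | PTX | Placebo | Does frequency reveal the arm? |
|---|---|---|---|
| above 50 | 3 × 14 = 42 | 42 | No |
| 10-50 | 2 × 14 = 28 | 42 | Yes |
| below 10 | 1 × 14 = 14 | 42 | Yes |

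One or two capsules a day occurs only on PTX, so frequency alone is enough for someone who knows the rule. Three a day occurs in both arms. It points to placebo only when it is read together with an eGFR of 50 or below.

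**Step 2: can eligible subjects have eGFR of 50 or below?** The documents name no eGFR equation, so this step is an assumption: CKD-EPI 2021 or MDRD, ages 40, 55 and 70, both sexes. The exclusion limit of 4.0 in Table 1 is printed in g/dL and read here as mg/dL.

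| Quantity | CKD-EPI 2021 | MDRD |
|---|---|---|
| Creatinine at which eGFR is 50 (mg/dL) | 1.17-1.75 | 1.08-1.55 |
| eGFR at creatinine 1.8 | 29.9-48.2 | 27.8-42.0 |
| eGFR at creatinine 4.0 | 11.5-18.5 | 11.1-16.7 |

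On this grid every subject who enters with creatinine from 1.8 to 4.0 mg/dL is in the 10-50 band, and none is below 10 at entry (an eGFR of 10 needs a creatinine of about 4.37 or more). The grid does not cover all eligible ages. A man of 20 with creatinine 1.8 has a CKD-EPI 2021 eGFR of about 55.

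**Step 3: how many subjects?** If a share p of the 30 has eGFR of 50 or below, the schedule is revealing for 30p of them, across both arms. The documents do not give p. For illustration, p = 25%, 50% and 75% give 7.5, 15 and 22.5, or about 8, 15 and 23 subjects. These are multiples of chosen shares, not estimates.

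**Step 4: the section 2 sentence taken literally.** At eGFR 10-50 it gives 42 × 400 mg = 16.8 g over 14 days, against 28 × 400 mg = 11.2 g under the tiers: 16.8 / 11.2 = 1.5.

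**Step 5: after the fix.** With tiered placebo, both arms take 42, 28 or 14 capsules in the three bands. Within a band, frequency then carries no information about the arm.

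**The case against.** **The unblinding is inferred from one loosely built sentence.** The synopsis may have meant the tiers to cover placebo as well, and section 7.1 does not fix placebo at three times a day. The Investigational Pharmacy prepares the capsules and runs the randomization, so it could match frequencies within its existing procedures. This stands in part. A reader might infer that the blind will be broken in practice, and the documents do not show that. They do state a placebo frequency, and nowhere do they say that it follows eGFR.

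**The arm is revealed only to someone who knows the rule and, for placebo, the eGFR.** This is correct. The investigators would have both.

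**Section 2 is shorthand.** A reader might infer that the protocol orders full-dose PTX for subjects with reduced eGFR. The documents do not support this. Taken literally, the sentence would also abolish the placebo arm immediately after 1:1 randomization, and the hypothesis, the synopsis and section 7.1 all provide for renal dosing. It is a wording conflict and not the likely regimen.

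**The two problems do not add up.** If everyone took three doses a day, frequency would reveal nothing. If the synopsis were followed, nobody would exceed the tiered dose. They are alternatives.

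**The effect on results is limited.** A laboratory endpoint resists assessor bias. Grade 3 relatedness is not left to the investigator alone, because section 7.2 has a medical monitor conduct an independent review. Both safeguards are real and reduce the weight of the point. Neither covers the start of dialysis or the choice of concurrent drugs.

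**Conclusion.** The concern holds as a gap in the blinding rules. The synopsis fixes placebo at three times a day, PTX frequency falls with eGFR, and no text matches the two. Followed as written, frequency with eGFR identifies the arm for any subject with eGFR of 50 or below (28 or 14 capsules against 42) and for nobody above 50.

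The number of subjects affected cannot be taken from the documents. Under the assumed equations and ages, creatinine from 1.8 to 4.0 mg/dL puts a subject in the 10-50 band at entry, so the group is unlikely to be empty. The likely bias in the primary endpoint is small. The more exposed items are dialysis start, co-medication and, to a lesser degree, adverse event relatedness.

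The section 2 sentence is a secondary wording conflict, worth a factor of 1.5 in dose at eGFR 10-50 only if someone doses from it and ignores section 7.1. This should be fixed, and the remedy is simple.

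**What to change.** 1. **Brief Study Synopsis and section 7.1:** state that the Investigational Pharmacy applies the same eGFR-based frequency to PTX and placebo: three times a day above 50, twice a day at 10-50, once a day below 10.
2. **Section 2:** replace the dosing sentence with wording such as: *study drug (PTX 400 mg or matching placebo) for 14 days at the eGFR-based frequency in section 7.1.*

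The cost is wording in three places. The pharmacy must also set placebo frequency by eGFR, which is a small extra task. Population, endpoints and sample size do not change.
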